6.4 Overall Survival (OS)

OS is defined as the number of months from randomization to date of death from any cause. Patients who are alive or lost to follow-up as of a data analysis cutoff date will be right-censored.

$$\text{OS (months)} = (\text{Date of Death/Censoring} - \text{Date of Randomization} + 1) \div 30.4375$$

6.5 Duration of Response (DOR)

DOR is defined as the number of months from the date where a CR / PR (based on RECIST 1.1) or irCR / irPR (based on irRECIST) was firstly observed, to the first date that recurrent or progressive disease is documented. DOR will be calculated for patients who achieved a confirmed CR / PR or irCR / irPR. The same censoring rules for primary analysis will also apply here for patients who achieved a confirmed CR / PR or irCR / irPR. Patients with no baseline or post-baseline assessments will not be analyzed.

$$\text{DOR}_{RECIST\ 1.1} \text{ (months)} = (\text{Date of Progressive Disease} - \text{Date of CR/PR} + 1) \div 30.4375$$

$$\text{DOR}_{irRECIST} \text{ (months)} = (\text{Date of Progressive Disease} - \text{Date of irCR/irPR} + 1) \div 30.4375$$

6.6 Time to Response (TTR)

TTR is defined for the subset of patients that achieve best overall response of confirmed CR/PR or confirmed irCR/irPR as the number of months from date of randomization to date of the initial documented response of CR/PR (based on RECIST 1.1) or irCR/irPR (based on irRECIST).

**Statistical Analysis Plan
SNDX-275-0602 (TRIO025)
DM-025-037**

$TTR_{RECIST\ 1.1} \text{ (months)} = (\text{Date of CR/PR} - \text{Date of Randomization} + 1) \div 30.4375$

$TTR_{irRECIST} \text{ (months)} = (\text{Date of irCR/irPR} - \text{Date of Randomization} + 1) \div 30.4375$

6.7 Dose-limiting Toxicity (DLT)

DLT is defined as the occurrence of specific events defined in Section 9.6 of the protocol within the first cycle of treatment (i.e. between Day 1 to Day 21 of Cycle 1) of entinostat in combination with atezolizumab that are considered by the investigator to be at least possibly related to study drug using the National Cancer Institute (NCI) Common Terminology Criteria for Adverse Events (CTCAE) version 4.03.

6.8 Maximum Tolerated Dose (MTD)

MTD is defined as the highest dose level at which < 33% of 6 patients experience DLT.

6.9 Recommended Phase 2 Dose (RP2D)

RP2D will be equal to or less than the preliminary MTD. This will be determined in discussion with the sponsor, the study medical monitor and dose determination phase investigators.

6.10 Treatment Emergent Adverse Events (TEAEs)

TEAEs is defined as AEs that start on or after the first administration of study treatment or AEs that start before the first administration of study treatment but worsened after study treatment is initiated.

6.11 Other Definitions

6.11.1 Baseline

The last available assessment done on or before the date of first dose of study treatment.

If patients have no value as defined above, the baseline value will be missing.

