- If radiologic imaging demonstrates initial evidence for PD, tumor assessment should be repeated at the earliest of 4 weeks, or preferably on the study schedule of 6 weeks, in order to confirm PD.

⁷ Performed only if radiological progression was not previously observed on study.

⁸ For female patients of child-bearing potential, a required serum pregnancy test is to be performed during screening and a urine test within 3 days before the first study drug dose. Pregnancy testing is to be repeated during the study any time pregnancy is suspected.

⁹ Analytes tested: RBC, WBC with absolute counts of individual cell types, platelet count, HGB and HCT. Screening only also includes: prothrombin time (PT) or international normalized ratio (INR) and activated partial thromboplastin time (aPTT). ¹⁰ Analytes tested: ALT, AST, albumin, alkaline phosphatase, total bilirubin, BUN, calcium, creatinine, sodium, potassium, chloride, bicarbonate, glucose, LDH, phosphorus, total protein and uric acid. Magnesium and TSH at enrollment only, unless clinically indicated.

¹¹ Performed only if screening laboratory tests performed >7 days prior to enrollment; screening laboratory results remain as the baseline entry criteria and abnormalities thereafter are to be noted as, and treated as, adverse events

¹² Samples collected pre-dose; not collected after C3 D1 except at EOT.

¹³ Samples collected pre-dose.

¹⁴ Sample taken before any study drug administration.

¹⁵ Fresh tumor core biopsy during screening from all patients on a mandatory basis; required on C2D15 (+/-3 days) until 20 samples are obtained in the Phase 2, but optional for everyone else; optional for all patients at disease progression and end of study treatment. Archival tissue is collected at screening when available.

¹⁶ The initial dose of atezolizumab will be delivered over 60 (\pm 15) minutes. If tolerated without infusion-associated adverse events, the second infusion may be delivered over 30 (\pm 10) minutes and if well tolerated, all subsequent infusions as well. Vital signs should be determined up to 60 minutes before each infusion as well as during and after infusion if clinically indicated.

¹⁷ C1D1 samples are taken pre-dose and 2-4 h post entinostat dosing; C1D8 and C1D15 taken any time after entinostat dosing; C2D1 taken pre-dose

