9.2.2 Dosing and Administration

All patients will self-administer entinostat/placebo PO once weekly on study days 1, 8 and 15 of each 21 day cycle. A new bottle of entinostat/placebo will be dispensed on day 1 of each cycle, regardless of the number of pills remaining in the bottle from the previous cycle.

On study days on which patients receive both entinostat/placebo and atezolizumab, entinostat/placebo is to be taken prior to atezolizumab.

Entinostat/placebo is to be taken on an empty stomach, at least 2 hours after a meal and at least 1 hour before the next meal.

If an entinostat/placebo dose is missed, it may be taken up to 48 hours after the scheduled dosing time. If it is not taken within the 48 hour window, the dose should not be taken and will be counted as a missed dose. The patient should take the next scheduled dose per protocol. Missed doses should be noted as such on the patient drug diary and in the eCRF.

If entinostat/placebo is vomited, dosing should not be re-administered but instead the dose should be skipped.

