9.3.2 Dosing and Administration

The dose level of atezolizumab in this study is 1200 mg administered by IV infusion q3w.

Administration of atezolizumab will be performed in a setting with emergency medical facilities and staff who are trained to monitor for and respond to medical emergencies.

The initial dose of atezolizumab will be delivered over 60 (± 15) minutes. If the first infusion is tolerated without infusion-associated adverse events, the second infusion may be delivered over 30 (± 10) minutes. If the 30-minute infusion is well tolerated, all subsequent infusions may be delivered over 30 (± 10) minutes, otherwise it should be delivered over 60 (± 15) minutes. The patient's vital signs (heart rate, respiratory rate, blood pressure, and temperature) should be determined no more than 60 minutes before each atezolizumab infusion. Vital signs should also be obtained during or after the atezolizumab infusion if clinically indicated.

No premedication will be allowed for the first dose of atezolizumab. Premedication may be administered for subsequent infusions at the discretion of the treating physician after consultation with the Medical Monitor.

Any overdose or incorrect administration of study drug should be noted on the Study Drug Administration electronic eCRF. Adverse events associated with an overdose or incorrect administration of study drug should be recorded on the Adverse Event eCRF.

Refer to the Pharmacy Manual for complete details regarding supply, storage, accountability, and destruction of Atezolizumab.

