6.11.2 Date of First Dose

The date of first dose (of study drug) is derived as the first date when a nonzero and nonmissing dose of study drug is administered. This can also be referred to as the start of the study treatment.

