10.9.4 Laboratory Values

Hematology and serum blood chemistry will be summarized in descriptive statistics by calculating the mean, standard deviation, median, and range for the following:

- Baseline value
- Minimum post baseline value
- Maximum post baseline value
- Average post baseline value
- Last post baseline value

Laboratory values will be assigned toxicity grade when available using NCI CTCAE version 4.03. Shift tables in laboratory toxicity grades (comparing baseline grade with worst post-baseline grade) will be analyzed using standard shift tables, presenting number and proportion of patients and their maximum grade shift.

For laboratory tests without a toxicity grading scale, the shift table will present directional shifts from baseline to above or below the laboratory standard normal range using the maximum increase and/or decrease observed throughout the course of treatment/observation.

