10.9.6 Vital Signs

Vital sign measurements will be summarized by descriptive statistics in the same manner described for laboratory values.

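### Baseline is set by calendar date, so vital signs taken during or after the first infusion, if captured, fall on the baseline side and drop out of the post-baseline summaries

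*SAP*

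**What the plan says.** SAP 6.11.1 gives one baseline rule for all assessments: "The last available assessment done on or before the date of first dose of study treatment". SAP 6.11.2 makes the anchor a date as well; it is "derived as the first date when a nonzero and nonmissing dose of study drug is administered".

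Protocol 9.3.2 says that vital signs "should be determined no more than 60 minutes before each atezolizumab infusion", and adds: "Vital signs should also be obtained during or after the atezolizumab infusion if clinically indicated". Footnote 16 of Table 1-1 repeats this: "Vital signs should be determined up to 60 minutes before each infusion as well as during and after infusion if clinically indicated". Neither place exempts the first infusion.

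For days on which both drugs are given, protocol 9.2.2 states that "entinostat/placebo is to be taken prior to atezolizumab". Protocol section 10 starts both on C1D1.

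On analysis, SAP 10.9.6 says: "Vital sign measurements will be summarized by descriptive statistics in the same manner described for laboratory values". SAP 10.9.4 lists five summaries for laboratory values: the baseline value, then the minimum, maximum, average and last values after baseline. The planned vital-signs table in SAP 11.1 has the same five.

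**The concern.** A reading prompted by a problem at the first infusion is taken on the date of first dose, later than the routine pre-infusion reading. A rule that looks only at the date, and takes the last value on it, selects that reading as baseline. The misclassification is selective, because it arises only when someone judged a same-day recheck necessary.

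At stake are the tables meant to show acute changes in vital signs. Under protocol 10.2.3, vital signs during treatment are scheduled only on day 1 of each cycle. The next scheduled reading after C1D1 is therefore at C2D1, nominally 21 days later, and cannot recover what happened at the first infusion.

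The rule also sits oddly beside neighbouring definitions. SAP 6.10 ties treatment-emergent events to the first administration. Protocol 13.3 asks for a safety assessment after dosing, not after the dosing date.

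**Working it through.** The plan gives no figure to reproduce. The check applies the baseline rule literally to the readings that the protocol allows on C1D1.

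**Step 1: what falls on the date of first dose.** Entinostat/placebo and the first infusion are both given on C1D1. The pre-infusion reading and any reading during or after the infusion therefore share that date.

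**Step 2: which reading is baseline.** Call the pre-infusion reading *p*, the readings during or after the infusion *r1* to *rk* in time order, and the readings from later dates *v1* to *vn*. All of *p*, *r1* … *rk* satisfy the rule. The last available is *rk*, so baseline = *rk*.

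**Step 3: what is post-baseline.** The SAP does not define this term separately; I read it as later than the baseline assessment. Nothing on C1D1 is later than *rk*, so only *v1* … *vn* qualify. Readings *r1* to *rk-1* count neither as baseline nor as post-baseline.

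**Step 4: when the summaries change.** A pre-dose rule would give baseline = *p* and post-baseline = {*r1* … *rk*, *v1* … *vn*}. Against that:
- baseline differs unless *rk* = *p*;
- the item listed as "Minimum post baseline value" differs when any *r* lies below every *v*, and the maximum differs when any *r* lies above every *v*;
- the average differs unless the mean of the *r* values equals the mean of the *v* values;
- the last value is unchanged if there is any later reading.

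**Step 5: an illustrative record.** The values are invented, not taken from the documents. Systolic pressure is 128 before the infusion, 84 during a reaction, 96 afterwards and 126 at C2D1, with no later readings.

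| Summary (mmHg) | Rule as written | Pre-dose rule |
|---|---|---|
| Baseline | 96 | 128 |
| Minimum post-baseline | 126 | 84 |
| Maximum post-baseline | 126 | 126 |
| Average post-baseline | 126 | (84 + 96 + 126) / 3 = 102 |
| Last post-baseline | 126 | 126 |

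Setting this patient's minimum against her baseline gives 126 − 96 = +30 under the rule as written and 84 − 128 = −44 under a pre-dose rule.

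**Step 6: is it corrected elsewhere?** I found no clock time, pre-dose condition or exception for unscheduled readings elsewhere in the protocol or SAP.

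**The case against.** The best defence concerns reach and consequence, and much of it stands.

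- **Data capture.** Readings during or after an infusion are unscheduled. The documents do not say whether the eCRF collects them or their times. If they are not collected, nothing goes wrong. If they are collected without a time, the last one on the date cannot be identified. This stands: the point is conditional.
- **No change table.** A reader might infer from the +30 against −44 comparison that the trial would report a false rise in blood pressure. The documents do not support that. SAP 11.1 plans five group summaries for vital signs. Shift tables are planned for laboratory values and ECOG status, not for vital signs. The record shows the mechanism only.
- **Other routes.** A reader might infer that first-infusion reactions disappear from the safety record. They do not. SAP 11.2 lists every vital-sign result. A reaction reported as an adverse event is treatment-emergent under SAP 6.10. Events suggestive of infusion-related reactions are of special interest under protocol 12.4.3 and go to the sponsor within 24 hours.
- **Number of patients.** A reader might assume that 5–10% have such readings, which would be 0.05 × 70 = 3.5 to 0.10 × 70 = 7 Phase 2 patients. Nothing in the documents supports that range, and an extra reading close to the pre-infusion value changes the summaries very little.
- **Laboratory tests.** The wording would also catch a test repeated after dosing on C1D1. No post-dose safety laboratory test is scheduled that day, however, so this remains hypothetical.

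None of this changes what the rule does to a captured reading. It limits where the effect shows.

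**Conclusion.** The point holds in a limited form. Read literally, SAP 6.11.1 turns the last C1D1 vital-sign reading into baseline, even when it follows dosing. It also keeps every C1D1 post-dose reading out of the minimum, maximum and average post-baseline summaries.

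This rests on two assumptions: that such readings are in the database with enough information to order them, and that post-baseline means later than the baseline assessment. The number of patients is unknown.

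Only descriptive safety summaries are affected. PFS, OS and response are not. A reader might infer a bias towards one arm; the documents do not establish one, since both arms receive atezolizumab. This is a minor correction to a definition, worth making because the rule gives a wrong result in the patients for whom a same-day recheck mattered.

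**What to change.** Replace the definition in SAP 6.11.1 with one that contains four elements:

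1. Baseline is the last non-missing pre-dose assessment, identified by clock time or by the scheduled time-point label.
2. For vital signs, the scheduled C1D1 pre-infusion reading qualifies as baseline even if it was taken after that day's entinostat/placebo dose.
3. Every reading during or after the first infusion is post-baseline.
4. Where no time is recorded, a C1D1 value is accepted as baseline only if it is the scheduled pre-dose assessment.

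The second element is needed because entinostat/placebo is taken first and the vital signs may be taken up to 60 minutes before the infusion. A bare cut at the first dose of either drug could therefore disqualify a routine pre-infusion reading in any patient, and would leave it unclassified if only readings during or after the infusion were named as post-baseline.

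The cost is a short change to the SAP text and the matching derivation. It relies on a time or time-point label on the eCRF, which the documents do not confirm. The one small downside is that a C1D1 vital-sign baseline may follow the entinostat/placebo dose by a short interval. No change to dosing or to the visit schedule is involved.

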6.11.2 Date of First Dose

The date of first dose (of study drug) is derived as the first date when a nonzero and nonmissing dose of study drug is administered. This can also be referred to as the start of the study treatment.

6.11.3 Date of Last Dose

The date of last dose (of study drug) is derived as the last date when a nonzero and nonmissing dose of study drug is administered.

6.11.4 Last Contact Date

The last contact date will be derived for patients not known to have died at the analysis cut-off using the latest complete date among the following dates which precede the cut-off date:

- All assessment dates (e.g. vital signs assessment, performance status assessment, tumor assessments, etc.)
- Date patient was last known alive
- Start and stop dates of concomitant medications
- Start and stop dates of adverse events
- Date of last dose
- Date of registration (Phase 1b)/randomization (Phase 2)

7. STUDY POPULATION

7.1 Full Analysis Set (FAS)

The **Full Analysis Set (FAS)** includes all patients who were enrolled (for Phase 1b) or randomized (for Phase 2) to study treatment, regardless of whether they actually received study medication. All efficacy analyses will be evaluated based on data from this population set according to the treatment group they were assigned to at registration/randomization and based on the strata they were originally assigned to at the time of randomization. This population set will be identified using the FASFL (Full Analysis Set Population Flag) as defined in Subject-Level Analysis Dataset (ADSL) according to Analysis Data Model (ADaM).

7.2 Per-protocol Analysis Set

The **Per-protocol Analysis Set** consists of all patients who were enrolled/randomized and did not have any important deviations (i.e. excludes patients with important deviations from FAS). The list of patients who are identified with important deviations will be provided to biostatistician(s) by TRIO Project Management. This population set will be identified using the PPROTFL (Per-Protocol Population Flag) as defined in ADSL according to ADaM.

7.3 Safety Analysis Set

The **Safety Analysis Set** consists of all patients who receive any study treatment, and will be used for the analysis of safety data in both Phase 1b and Phase 2 portions of the study. This population will be based on the first dose received at cycle 1, if this differs from that to which the subject was randomized and will be used for the analysis of safety data. This population set will be identified using the SAFFL (Safety Population Flag) as defined in ADSL according to ADaM.

8. INTERIM ANALYSIS AND EARLY STOPPING RULE

One interim safety analysis is planned during the Phase 2 of the study after the first 20 patients are treated for one cycle. As mentioned in section 5.3.2, the result of this analysis will be reviewed by DSMB who will act in an advisory capacity to the Sponsor with respect to safeguarding the interests of trial patients and assessing the safety of the interventions administered during the trial. As per Section 13.2 of the protocol, an interim efficacy analysis is performed when 45 PFS events are observed to support the Sponsor's product development plans and ongoing resourcing activities. Although there are no plans to terminate the study early, the DSMB will review the results and decision will be made in collaboration with the Sponsor as well as the Steering Committee should the study needs to be terminated.

9. DATA SCREENING AND ACCEPTANCE

9.1 General Principles

For the planned analyses, data acceptance will be based on the creation and review of the tables, listings, and figures (TLF) in collaboration with Data Management and Project Management according to TRIO Standard Guideline SG8.1 "Validation of Statistical Analysis". In general, TLF programs will be created prior to a database snapshot or database lock. Dry run(s) of TLF programs will be done in order to review for extreme, unusual, and missing values. Such cases will be identified to Data Management and Project Management for further investigation and potential resolution prior to a snapshot or lock of the database. As data issues are detected, additional procedures might be needed in order to ensure resolution in subsequent data transfer(s).

For the final analysis, all procedures will be run to ensure previously identified data issues have been resolved. The TLF programs will also be run and the outputs will be reviewed to ensure no further data issues are found.

9.2 Unblinding Plan

For the Phase 2 Expansion Phase of this study, all TRIO personnel will be blinded. At the time of statistical analysis, only the Independent Statistician, who does not work on the study directly, will be unblinded. He/she will obtain the unblinded randomization file as well as unblinded medication list in order to unblind the data and perform the analysis accordingly. All relevant unblinded files will be stored separately on the network and access to the unblinded data will be restricted to the Independent Statistician only. Refer to TRIO Standard Operating Procedure SOP 5.7 “Blinding and Unblinding”.

9.3 Data Handling and Electronic Data Transfer

All clinical data will be entered directly by the designated users at the site into the database using Oracle Clinical Remote Data Capture (OCRDC) according to electronic Case Report Form (eCRF) and will be extracted in the form of raw SAS® datasets by Data Management. Data extracts will be provided to biostatistician(s) on a regular basis. Once the final data queries have been generated and resolved, the database will be deemed “locked” and final database extract will be performed after official data snapshots are completed. The data used for all the analyses will be archived.

9.4 Handling of Incomplete and Missing Data

Missing and incomplete data will be identified for investigation, and possible resolution, by Data Management and Project Management prior to an official database snapshot or database lock through review of TLF.

Missing Data: All analyses and descriptive summaries will be based on the reported data. Unless otherwise specified, missing data will not be imputed or “carried forward.”

Partial or Missing Date for Adverse Events and Concomitant Medications:

Imputation Rules for Partial or Missing Stop Dates:

If the month and year are present, impute the last day of that month.

If only the year is present, impute December 31 of that year.

If the stop date is entirely missing, assume the event or medication is ongoing.

If a partial or complete stop date is present and the ‘ongoing’ box is checked, then it will be assumed that the adverse event or concomitant medication stopped and the stop date will be imputed if partial.

**Statistical Analysis Plan
SNDX-275-0602 (TRIO025)
DM-025-037**

Imputation Rules for Partial or Missing Start Dates

Start Date		Stop Date						
		Complete: yyyymmdd		Partial: yyyyymm		Partial: yyyy		
		< 1 st dose	≥ 1 st dose	< 1 st dose yyyyymm	≥ 1 st dose yyyyymm	< 1 st dose yyyy	≥ 1 st dose yyyy	
Partial: yyyymm	= 1 st dose yyyymm	2	1	2	1	n/a	1	1
	≠ 1 st dose yyyymm		2		2	2	2	2
Partial: yyyy	= 1 st dose yyyy	3	1	3	1	n/a	1	1
	≠ 1 st dose yyyy		3		3	3	3	3
Missing		4	1	4	1	4	1	1

1 = Impute the date of first dose

2 = Impute the first of the month

3 = Impute January 1 of the year

4 = Impute January 1 of the stop year

